8.2 SAFETY ASSESSMENTS

Safety assessments are not conducted as a part of this protocol.

See **Section 10.1** for Safety Oversight Details.

8.3 ADVERSE EVENTS AND SERIOUS ADVERSE EVENTS

8.3.1 DEFINITION OF ADVERSE EVENTS

This protocol uses the definition of adverse event from 21 CFR 312.32 (a): any untoward medical occurrence associated with the use of an intervention in humans, **whether or not considered intervention related. Any medical or psychiatric condition that is present or within the expected trajectory of the child's chronic condition at the time that the participant is screened will be considered as baseline and not reported as an AE.**

8.3.3.1 SEVERITY OF EVENT

For adverse events (AEs) not included in the protocol defined grading system, the following guidelines will be used to describe severity.

- **Mild** Events require minimal or no treatment and do not interfere with the participant's daily activities.
- **Moderate** Events result in a low level of inconvenience or concern with the therapeutic measures. Moderate events may cause some interference with functioning.
- **Severe** Events interrupt a participant's usual daily activity and may require systemic drug therapy or other treatment. Severe events are usually potentially life-threatening or incapacitating. Of note, the term "severe" does not necessarily equate to "serious".

8.3.3.2 RELATIONSHIP TO STUDY INTERVENTION/EXPERIMENTAL MANIPULATION

All adverse events (AEs) will have their relationship to study procedures, including the intervention, assessed by an appropriately trained clinician based on temporal relationship and his/her clinical judgment. The degree of certainty about causality will be graded using the categories below.

- **Definitely Related** There is clear evidence to suggest a causal relationship, and other possible contributing factors can be ruled out. The clinical event, including an abnormal laboratory test result, occurs in a plausible time relationship to study procedures administration and cannot be explained by concurrent disease or other drugs or chemicals. The response to withdrawal of the study procedures should be clinically plausible. The event must be pharmacologically or phenomenologically definitive.
- **Probably Related** There is evidence to suggest a causal relationship, and the influence of other factors is unlikely. The clinical event, including an abnormal laboratory test result, occurs within a reasonable time after administration of the study procedures, is unlikely to be attributed to concurrent disease or other drugs or chemicals, and follows a clinically reasonable response on withdrawal.
- **Potentially Related** There is some evidence to suggest a causal relationship (e.g., the event occurred within a reasonable time after administration of study procedures). However, other factors may have contributed to the event (e.g., the participant's clinical condition, other concomitant events). Although an AE may rate only as "possibly related" soon after discovery, it can be flagged as requiring more information and later be upgraded to "probably related" or "definitely related", as appropriate.
- **Unlikely to be related** A clinical event, including an abnormal laboratory test result, whose temporal relationship to study procedures administration makes a causal relationship improbable (e.g., the event did not occur within a reasonable time after administration of the study procedures) and in which other drugs or chemicals or underlying disease provides plausible explanations (e.g., the participant's clinical condition, other concomitant treatments).
- **Not Related** The AE is completely independent of study procedures administration, and/or evidence exists that the event is definitely related to another etiology. There must be an alternative, definitive etiology documented by the clinician.

8.3.3.3 EXPECTEDNESS

A clinician with appropriate expertise will be responsible for determining whether an adverse event (AE) is expected or unexpected. An AE will be considered unexpected if the nature, severity, or frequency of the event is not consistent with the risk information previously described for the study procedures.

8.3.4 TIME PERIOD AND FREQUENCY FOR EVENT ASSESSMENT AND FOLLOW-UP

The occurrence of an adverse event (AE) or serious adverse event (SAE) may come to the attention of study personnel during study visits and interviews of a study participant presenting for medical care, report from an involved clinician, or upon review by a study monitor.

All AEs, not otherwise precluded per the protocol, will be captured on the appropriate case report form (CRF). Information to be collected includes event description, time of onset, clinician's assessment of severity, relationship to study procedures (assessed only by those with the training and authority to make a diagnosis), and time of resolution/stabilization of the event. All AEs occurring while on study will be documented appropriately regardless of relationship. All AEs will be followed to adequate resolution. Any medical or psychiatric condition that is present or within the expected trajectory of the child's chronic condition at the time that the participant is screened will be considered as baseline and not reported as an AE. Changes in the severity of an AE will be documented to allow an assessment of the duration of the event at each level of severity to be performed. Documentation of onset and duration of each episode will be maintained for AEs characterized as intermittent. The project manager will record events with start dates occurring any time after informed consent is obtained until 7 (for non-serious AEs) or 30 days (for SAEs) after the last day of study participation. At each monthly assessment, the research staff or caregiver self-administered questionnaire will inquire about the occurrence of AE/SAEs since the last month. Events will be followed for outcome information until resolution or stabilization.

In our consent materials, we will describe the specific procedures for handling each of the types of potential incident. These procedures will be based on those in previous projects and include:

1. The staff member who suspect or learns of any adverse event will immediately begin the adverse event case report form in REDCap.
2. The staff member who suspects or learns of any adverse event will immediately contact the project manager and PI / site PI who in turn will make an immediate judgment as to whether to report it to the authorities or whether additional action is warranted to protect the child's or participant's safety.
3. The PI will decide on a course of action, consulting with an attorney and expert consultants as necessary. This course of action will usually follow the clinic's existing guidelines and practices, with consideration of any pertinent legal or ethical issues related to it. For instance, a clinician would normally carry out child abuse reporting after it is deemed necessary. The course of action undertaken will be documented on the adverse CRF.
4. Serious adverse events (e.g., suicidal intent, child abuse reporting) will be reported immediately to the IRB and Safety Monitoring Committee, per their reporting guidelines, whereas more mild adverse events (e.g., mild distress following survey administration or coaching) will be compiled on an annual basis and reported to the IRB.
5. The Data Monitoring Committee will review all adverse event reports and determine whether additional steps are necessary (See **Section 10.1**)
6. As part of the informed consent process, study staff will provide subjects and their parent/guardian a specific name and phone number of a person to contact in case of an adverse event.

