1.2 SCHEMA

1.3 SCHEDULE OF ACTIVITIES

	STUDY PERIOD							
	Enroll- ment Visit	REPACT Intervention Period						Final Visit
Personnel involved	Research Coordina- tor	Clinicians						Research Coordina- tor
Month	0	1	2	3	4	5	6	End of Month 6
Timepoint	T ₀	T ₁	T ₂	T ₃	T ₄	T ₅	T ₆	T ₇
Confirm eligibility	X							
Informed Consent	X							
Baseline Assessment	X							
6-month Assessment								X
Randomization	X							
Subject Payment	X							X
Usual comprehensive medical care and coordination via Complex Care Program		X	X	X	X	X	X	
Intervention Arm Only								
Text Msg Training	X							
Weekly mHealth text message and response		X	X	X	X	X	X	
Intervention overview		X						
Create action plan		X						
Action planning		X	X	X	X	X	X	
JIT coaching		X	X	X	X	X	X	
Monthly study assessments		X	X	X	X	X	X	

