RCT participants in both groups will undergo assessments of demographic, clinical and caregiving measures reported through questionnaire and medical record review at baseline at 6 months after enrollment. Feasibility, acceptability and fidelity data will be collected through parent-report, medical record review, and research team logs monthly during the intervention, and, for control group participants, at 6 months after enrollment.

Data about research participants (children and their families) will be collected by study research assistants through electronic self-administered questionnaires or structured interviews with parents either over the phone or in person, abstraction of child medical record data by the study RAs, and (for intervention group families) through phone interactions and direct observation with health coaches in RE-PACT. Content of these assessments include parent-report questions about child and parent health, parent perceptions of child health, family socio-demographic information, care utilization, and experiences of caregiving.

Analyses will assess feasibility, acceptability, fidelity and effect size estimates (by comparing numbers of respiratory exacerbations between intervention and usual care groups). We will use pre-specified definitions of success for each of our feasibility, acceptability and fidelity measures. We anticipate being underpowered to assess the efficacy of the intervention in this pilot study, but to inform a future large RCT we will test differences between intervention and active groups in the primary and secondary clinical outcomes. For each of these measures, we will compare differences between intervention and active control group outcomes at 6 months controlling for their baselines. While we anticipate that the intervention and control groups will be similar due to random assignment, we will adjust for any variables in our analysis that are not equal between the groups given the small sample size. In addition, we will analyze for any effect of primary home language on the study outcomes, as this may affect families’ ability to navigate systems of care in the U.S. To explore theoretical intervention mechanisms, we will also test the mediating effect of caregiver capability, opportunity, and motivation measures on the relationship between intervention and respiratory illness outcomes.

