5.5 STRATEGIES FOR RECRUITMENT AND RETENTION

Recruitment

We will recruit caregivers of children with severe CP between 0-17 years old. We will recruit a total of n=90 participants (n=45 at each site) divided across 3 waves. In each wave, there is a 1-2 month enrollment period. We anticipate approximately 80% of those screened will enroll, requiring approximately 110 individuals to be screened.

Potential participants will be identified by reviewing the clinic registries and/or EHR data using diagnostic codes for CP (ICD-10 G80-83), which contain detailed information about children and their diagnoses. We will send an “opt-out” letter that alerts families that a research study is being conducted and their child may be eligible, with a contact number to call if they wish to opt out of the research or if they wish to receive additional information or have any questions. Potentially eligible caregivers will be contacted by phone to screen for eligibility and interest.

If the research team is not notified that a family wishes to opt-out the research, the study research personnel will attempt to call the families (or meet them at an upcoming visit) to complete screening, informed consent, baseline questionnaires and random group assignment. Eligibility criteria for caregivers are detailed in **Study Population, Section 5.1-5.2**, and include being self-identified English- or Spanish-speaking caregivers of children with severe CP who have respiratory needs. CP status and additional eligibility criteria will be determined with a reliable and valid parent questionnaire and screener conducted at the beginning of initial phone contact.

Retention and Incentives

Study participants in this pilot RCT will be contacted at baseline (enrollment), monthly (for intervention subjects), and at 6 months (intervention and control groups). While we expect some degree of attrition will be inevitable, we will work to minimize attrition by sending regular follow-up post cards and phone calls requesting updates in contact information and also confirming or updating contact information when child medical records are reviewed. Moreover, participants will receive \$100 on study entry and exit.

Inclusion of Women and Minorities

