Just-in-time Adaptive Coaching Intervention Response. Coaching is accomplished by adapting PACT, which was initially adapted from the Care Transitions Intervention® (CTI),⁵⁰ to the pediatric population. The focus is: (1) medication self-management, (2) patient-centered records maintained by families, (3) timely follow-up, and (4) "red flags" and instructions how to identify/respond to them (i.e., action plans). Face-to-face visits are typically at the family's home; however, a neutral or "virtual" (telephone) visit is an option. Coaches review the four components, elicit goals, and focus coaching activities on needs identified by families. Phone calls discuss progress toward goals. This coaching approach provides the structure for JITAI activities.

Control Group. Those participants randomized to the control group will be provided usual care through the comprehensive clinical program at their children's hospital. They will also complete pre- and post-study assessments.

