Caregiver Strain	Survey	Caregiver Strain Questionnaire (CGSQ); ¹¹⁵ – mean global, objective, subjective scale scores Mental health (PHQ2) ¹¹⁶
Theory / Mechanism		
Capability	Survey	Family Caregiver Activation in Transition Measure (FCAT) ¹¹⁷ – mean composite score Caregiver General Self-Efficacy Scale (GSES) ¹¹⁸ – mean composite score
Opportunity	Survey	Family Experiences with Care Coordination (FECC) ¹¹⁹ - % top-box score for selected items
Motivation	Text logs	Confidence Responses mHealth texting (weekly score 1 through 10)

Assessment Procedures. Feasibility, acceptability and fidelity endpoint data will be collected during each of the three waves by research personnel reviewing study logs, conducting monthly chart reviews, and

administering surveys (by telephone, in person, or sending electronic self-administered links) with caregivers randomized to intervention. For active control groups participants, feasibility of assessments will be evaluated by completion rates at study exit. Caregiver and child measures above will be recorded at baseline, endpoints will be recorded at study exit (6 months after T0). Caregiving measures, which may change as a result of the intervention, will be collected at baseline and study exit. In addition, intervention and active control caregivers will be debriefed at study exit on their experiences in the study, and asked for feedback on the strengths, weaknesses and any concerns about the protocol. Between each wave and after the third wave, clinical teams at each site will be debriefed on strengths, weaknesses, and concerns about the protocol.

Reliability of Assessment Measures. The CP GMFCS measures and all the caregiving measures have been well-documented as reliable in the literature.^{11,74,115-119} We have separately established the reliability of identifying respiratory illnesses in our preliminary research (Kappa > 0.9). We will ensure reliability in data collection through direct observation, data auditing, establishing clear data dictionaries / definitions, using uniform variable definitions, and a central data repository coordinated and maintained by UW.

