The DMC members will review protocol-specific reports created by statisticians or delegates using data pulled from the REDCap data management tool. These standard reports will include an overview of study objectives, a review of actual and projected accrual rates, an evaluation of patient demographics for balance of randomization, and a summary of the number and seriousness of adverse events. An interim analysis of study results may be requested, and source documents may be reviewed to allow the DMC to independently judge whether the overall integrity and conduct of the protocol remain acceptable based on data provided and reported by the Principal Investigator.

In providing oversight for the conduct of this study, the ICTR DMC will meet every year during the 2-year study to review all adverse events. Additional meetings may be scheduled as determined by the DMC or as requested by the PI. There are no predefined stopping points for this study. All reportable events will be submitted to the DMC and the Health Services IRB in accordance with their reporting guidelines. The DMC will make recommendations to the Principal Investigator that could include actions of continuation, modification, suspension, or termination.

Adverse Event Protocol. The protocol for identifying and handling adverse events is outlined in **Section 8.3, Adverse Events and Serious Adverse Events** and will be revised with the DMC and included in the IRB application. Prior to the initiation of any data collection, the UW-ICTR DMC will review and approve the adverse event protocol.

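### The only scheduled adverse-event question falls at monthly assessments listed for the intervention arm, so AE ascertainment differs by arm and any between-arm AE count is open to detection bias

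*Combined protocol and SAP*

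**What the plan says.** Section 8.3.4 sets the timing of active safety enquiry: "At each monthly assessment, the research staff or caregiver self-administered questionnaire will inquire about the occurrence of AE/SAEs since the last month". It gives no other scheduled AE/SAE question, and none is written for the exit visit.

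Five places describe who has monthly contact:

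- Section 1.3 puts the monthly study assessments row under the heading "Intervention Arm Only".
- Section 5.5 plans monthly contact for intervention participants, and contact at baseline and 6 months for both groups.
- Section 4.1 collects feasibility, acceptability and fidelity data "monthly during the intervention, and, for control group participants, at 6 months after enrollment".
- Section 6.1.1 says of controls: "They will also complete pre- and post-study assessments".
- Section 8.1 describes "administering surveys (by telephone, in person, or sending electronic self-administered links) with caregivers randomized to intervention".

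Section 8.3.4 also lists routes that are not limited by arm: presentation for medical care, a clinician's report, monitor review, and a contact name and number given at consent. Any staff member who suspects or learns of an event must start an AE form at once.

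Under Section 10.1.6 the DMC reviews adverse events yearly, and its standard reports include "a summary of the number and seriousness of adverse events". Section 8.2 says that no safety assessments are conducted, and Section 9.4.4 (safety analyses) is marked not applicable.

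**The concern.** Followed as scheduled, the plan questions one arm every month and leaves the other to passive reporting. Intervention families also speak with coaches, who are bound by the duty to open an AE form. Events that may never reach a medical record, such as the mild distress after a survey that Section 8.3.4 gives as an example, are then more likely to be recorded, and recorded earlier, in the intervention arm.

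With no safety analysis planned and no predefined stopping points, AE review is a main input to any DMC recommendation to modify, suspend or terminate the trial. If counts are compared by arm, an apparent excess with RE-PACT could be an artefact of closer questioning. Equally, a real excess could be explained away as better ascertainment. This point is about AE ascertainment only, not the efficacy models.

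**Working it through.** The documents state no figure to reproduce here. The check is a cross-reading followed by simple arithmetic.

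**1. Which arm has monthly assessments?** Sections 1.3, 4.1, 5.5, 6.1.1 and 8.1 point to the intervention arm only. Four places carry no arm limit:

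- the synopsis (Section 1.1), which places outcome assessments at baseline and monthly;
- Section 6.5, which mentions monthly study calls;
- Section 7.3, which defines loss to follow-up partly by three missed monthly assessments;
- Section 9.4.3, whose between-arm longitudinal models use monthly assessments.

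The schedule and contact plan are the more specific texts, but the documents do conflict.

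**2. Scheduled monthly enquiries.** Section 9.2 gives 45 per arm, and Section 1.3 gives six monthly assessments.

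- Intervention: 45 x 6 = 270
- Control: 45 x 0 = 0

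**3. Delay to the next scheduled contact.** Assume events fall uniformly over 6 months. The mean lag is half the interval between contacts.

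- Intervention: 1/2 = 0.5 month
- Control: 6/2 = 3 months, to a visit at which no AE question is specified

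**4. Effect on recorded counts when true rates are equal.** Let p be the probability of passive capture (taken as equal in both arms), rM the capture of remaining events by monthly enquiry, and r6 their capture at the control exit visit. All three are assumptions; the documents give none.

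Ratio (intervention : control) = [1 - (1 - p)(1 - rM)] / [1 - (1 - p)(1 - r6)]

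With rM = 0.9:

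| p | r6 = 0 | r6 = 0.5 | r6 = 0.9 |
|---|---|---|---|
| 0.2 | 0.92/0.20 = 4.60 | 0.92/0.60 = 1.53 | 0.92/0.92 = 1.00 |
| 0.5 | 0.95/0.50 = 1.90 | 0.95/0.75 = 1.27 | 0.95/0.95 = 1.00 |
| 0.8 | 0.98/0.80 = 1.225 | 0.98/0.90 = 1.09 | 0.98/0.98 = 1.00 |

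The column r6 = 0 is the literal plan, with no AE question at exit. The column r6 = 0.9 leaves delay but no bias in counts. Coaching contact would raise p in the intervention arm and is not modelled.

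**5. With the same monthly question in both arms:** 270 enquiries per arm, a mean lag of 0.5 month in each and, with equal passive capture, an expected ratio of 1.0.

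**The case against.** The other side has a substantial case.

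- **Passive routes are open to both arms at any time.** A reader might infer that control events surface only at month 6. Section 8.3.4 does not support that: care encounters, clinician reports and caregiver calls can bring an event to light in any month. Section 5.5 adds follow-up postcards and phone calls without an arm limit, and Section 8.1 debriefs both arms at exit on concerns. None of these is a scheduled AE question, so the asymmetry remains.
- **Prompt reporting.** A reader might infer that control SAEs cannot meet the immediate-reporting rule. The duty starts when staff suspect or learn of an event, so late discovery does not breach it.
- **By-arm tables.** Section 10.1.6 states no split of AEs by arm, and Section 10.1.11 promises only that results will be submitted. That a biased comparison will be presented is an inference; the bias attaches to any comparison that is made.
- **False security.** The harm named in Section 2.3.1, later presentation with worse illness, should show in admissions, hospital days, ED visits and deaths. These are clinical outcomes, and Section 4.1 provides medical record review in both groups. This stands and limits the consequence. So does the exclusion, in both arms, of events within the child's expected trajectory.
- **Chart reviews.** Section 8.1 mentions monthly reviews, but for feasibility, acceptability and fidelity endpoints. It does not clearly extend them to controls or to AEs.
- **Conflicting text.** If the conflict over monthly assessments is resolved towards both arms, the gap closes. That supports reconciling the sections; it does not show that the schedule as written is adequate.

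**Conclusion.** The point holds in a limited form. On the schedule as written, active AE/SAE enquiry belongs to one arm, and no enquiry is specified at exit for either. Ascertainment therefore differs by arm, and a between-arm AE count could not be read at face value. The 270 against 0 counts planned questions; it does not measure bias. The range of about 1.0 to 4.6 is an illustration under assumed capture rates and equal true event rates, and 1.0 is reached only if exit capture in controls matches monthly capture. The primary feasibility, acceptability and fidelity endpoints are not at issue. The plan should be amended, because the remedy needs no new visits.

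**What to change.** First reconcile Sections 1.1, 6.5, 7.3 and 9.4.3 with Sections 1.3, 4.1, 5.5 and 6.1.1, and state whether controls have monthly assessments.

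- **If they do:** put the same AE/SAE question, with the same one-month look-back, to both arms.
- **If they do not:** add the same AE/SAE form, with 6-month recall, at the exit visit both arms already attend. Review charts for admissions, ED visits and deaths on one calendar in both arms. Base any between-arm AE count on these common sources only. Keep the monthly intervention-arm reports for prompt safety action, but tabulate them separately and label each event by source.

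In either case, state in Section 10.1.6 whether DMC tables are by arm.

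The second option costs one form at an existing visit and chart abstraction on a common calendar. Its limits should be stated. Recall of mild events over 6 months is weaker, so the comparison will rest mainly on chart-documented events. Charts may miss caregiver events. The exit form does not make control events known sooner. Intervention caregivers who have been asked every month may also recall more at exit, so some imbalance could remain.
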